#### Name and Description of Investigational Product or Intervention

Connect-Home Plus will introduce new organizational structure to support staff delivery of transitional care processes. Consistent with Donabedian, we anticipate that these changes in structure and care processes will be associated with improved patient and caregiver outcomes.(2) New elements of organizational structure include an EHR template, the Connect-Home Toolkit, and Staff Training protocols; we developed, refined and tested these, finding them to be feasible, acceptable, and associated with improved patient and caregiver experiences of care. After new structural elements are in place, SNF staff will use Connect-Home Plus care processes to deliver the 2-step transitional care intervention. In **Step 1**, SNF nurses, rehabilitation therapists, and social workers will develop a Transition Plan of Care and prepare the patient and caregiver to manage the patient's serious illness and functional needs at home. In **Step 2**, a home care RN will visit the patient and caregiver at home within 24 hours of discharge and the Dementia Caregiver Specialist will call the caregiver at home within 72 hours of the patient's discharge to home and up to two more times, within one month of the discharge to home.

#### Non-Clinical and Clinical Study Findings

The study is expected to have minimal risks, which are described below. Potential benefits are identified after the risks below.

#### Risks

**Physical Risks:** Patients and caregivers will receive transitional care in the SNF and in the patient's home. Transitional care activities involve verbal assessments, conversation, education, and planning. There is a possibility that participants could be fatigued from participation in the data collection activities. For example, while participating in a care-planning meeting, a patient might feel fatigued or need to take a break. Protection: If any participant has a physical injury, the study team will help them seek immediate medical attention. If a SNF patient or caregiver expresses fatigue during data collection, the data collection session will be terminated immediately, and a follow-up appointment scheduled.

**Psychological Risks:** Emotional distress related to learning more about medical and functional challenges and plans for care at home is a potential psychological risk. Staff in the SNF and in the home after discharge will engage patients and caregivers in conversations to plan strategies for managing illness at home. Also, during enrollment and data collection activities, staff will assess the patients' quality of life, functional mobility, falls at home, days at home without acute care use and caregivers' burden and distress related to the caregiving role. These study-related activities may also involve a chance for emotional distress. Protection: The study team will refer distressed patients and caregivers to their attending or primary care physicians for support with emotional distress.

**Social Risks:** During enrollment and data collection activities, study staff will collect data from participants about their health, function and quality of life; if others observed patients or caregivers participating in these activities, there is a chance that it could embarrass or distress patients or caregivers. Protection: The study team will recruit and collect baseline data for participants in a private room. When necessary, this data may also be obtained virtually when research personnel are not able to encounter face to face interactions with study participants. When these occasions arise, all virtual interactions will be conducted at a time when the patient is alone and not able to be overheard. Study team will conduct these in private settings as well ensuring that no questions and/or responses will be overheard. During telephone calls to collect outcome data, the identity of patients will be confirmed. All research staff will be trained by the PI and other study team members to collect data with the utmost respect and sensitivity to support participants and help them feel comfortable during data collection activities. The research team members will remind participants that participation in the study is voluntary, and that they have the right to withdraw from the study at any time if they are not comfortable. The team will assure patients and caregivers that withdrawal from the study will not have an impact on their medical care.

**Risk of Loss of Confidentiality:** During enrollment and data collection activities, staff will obtain health information about patients and caregivers. Thus, a potential risk to SNF patients and caregivers is loss of confidentiality. Protection: All research study personnel will be trained in IRB and HIPAA guidelines to maintain the security and confidentiality of the data. During the consenting process, the study team will explain the confidentiality protections and will inform the participants of their right to skip items, pause during participation, and withdraw from the study at any time. When face to face interaction is not feasible, study discussions will occur in a virtual manner. In order to avoid a loss of confidentiality, these interactions will be conducted in a private area where the discussions will not be overheard. Risks for loss of confidentiality will be minimal secondary to use of procedures to protect confidentiality, including (a) using study codes on data documents and keeping a separate document that links the study code to subjects' identifying information locked in a separate location and restrict access to this document to certain members of the study team; (b) de-identification of data to remove the possibility that data could be connected to individuals that consented to participate in the study; (c) encrypting identifiable data; and (d) securely storing data documents within locked locations. All identifying information will be destroyed at the earliest possible time following completion of the study. In addition, data will be reported in aggregate form, without identifying information by site or individual. Publications arising from the study will not contain personal information. All SNF patients or caregiver participants will continue to receive routine medical care from their health care providers throughout the study.

### **Potential Benefits**

The major potential benefit of this study is new knowledge about ways to improve outcomes for SNF patients with ADRD and/or their caregivers. The patients will receive valuable information, training and plans about their diagnosis, indicators of emerging medical problems, medications, treatments, advance care directives, follow-up appointments and studies, home care services, questions to ask their community physicians, strategies to avoid

falls at home, self-care at home in the context of the COVID-19 pandemic (when applicable), and discrepancies in their home medications that should be addressed with community or SNF physicians. Their family caregivers will also receive this information and training as well as training to support the patient and strategies to relieve stress and hardship related to the caregiver role. As a result of the research, we will discover the feasibility and acceptability of the Connect-Home Plus intervention. If the intervention is feasible and acceptable, this study will provide an evidence-based practice rationale for a clinical trial to determine the efficacy of the Connect-Home Plus intervention. It will also provide new knowledge related to care of adults with ADRD in the context of the COVID-19 pandemic.

### **Relevant Literature and Data**

SNF patients with ADRD are an under-studied population with very high risk for complications during care transitions and poor outcomes after discharge home.(3) Annually, 1.6 million older adults undergo episodes of care consisting of hospitalization followed by a “short stay” in a nursing home, where they use the Medicare SNF benefit for rehabilitation and nursing care. SNF patients typically are frail, dependent, and seriously ill: a) 100% have recent acute illness (e.g., hip fracture, heart failure, genitourinary and pulmonary infections with & without sepsis);(4, 5) b) 28-34% were treated in intensive care during the index hospital stay;(4, 6) and c) 29-43% had  $\geq 1$  hospitalizations in the year prior to the index hospitalization and SNF stay.(6, 7) About 36% of persons admitted to SNFs are diagnosed with dementia, although rates are probably higher given the number of undiagnosed cases of dementia.(8) A growing literature indicates that transitions in care are especially challenging in the population with ADRD, who frequently experience unmet needs, including: (1) informed and collaborating family caregivers to manage illness at home, (2) support to prevent delays in discovery of changes in health (e.g., respiratory infections), (3) follow-up referrals for medical care of dementia (e.g., diagnosis and treatment planning), and (4) transition planning to assure adequate nutrition, hydration, pain control, medication management and follow-up medical care.(9-11) Lacking these and other essential supports during transitions in care, persons with ADRD are especially vulnerable to poor health outcomes. In one study, 89.2% of persons with ADRD experienced  $\geq 1$  hospitalization per year(12) and 23% of persons with ADRD experienced rehospitalization within 30 days of returning home.(13) Furthermore, caregivers for persons with cognitive impairment (i.e., spouses, children, friends) often lack time, resources, and training to keep up with the mounting challenges of care at home.(14-16) Preparing patients and caregivers for the transition to home is urgently needed; yet, healthcare systems often provide suboptimal transitional care planning, and their staff lack expertise in dementia care.(17, 18) Thus, the proposed study is significant because it will extend SNF transitional care research to persons with ADRD and their caregivers.

This study will build on findings in an ongoing clinical trial of the Connect-Home intervention, which tests a transitional care intervention with high potential for adapting to the unique needs of persons with ADRD and caregivers.(19) The objective of the Connect-Home trial (ongoing) is to conduct a stepped-wedge cluster-randomized trial to test Connect-Home transitional care against standard discharge planning (control) using individuals discharged to home (N=360) and their caregivers (N=360) in 6 SNFs. The Specific Aims are to evaluate the efficacy of Connect-Home to improve: (1) SNF patient and caregiver preparedness for discharge (primary outcome, assessed 7 days after discharge), (2) patient quality of life, function, and acute care use, and (3) caregiver burden and distress (secondary outcomes assessed 30 and 60 days after discharge home). The setting is six SNFs and, for participants in the intervention arm, patient homes, where community-based RNs visit them within 24 hours of discharge. The Connect-Home Intervention involves new organizational structure, including: (1) the “Transition Plan of Care Template,” installed in the SNF EHR system, which staff use to record transitional care goals and deliver the intervention; (2) the “Connect-Home Toolkit,” a manual with standard procedures and tools; and (3) staff training to deliver transitional care processes that address key care needs of SNF patients and their caregiver. Connect-Home structures support transitional care processes in the SNF and the person’s home. In collaboration with the SNF patient and their caregiver, SNF nurses, social workers and

rehabilitation therapists (1) set goals for home-based care, (2) make plans for transition from SNF to home, and (3) make preparations for home-based care (e.g., teach symptom management). Following discharge, community-based RNs implement the transition plan (e.g., set-up new routines for self-care at home).(19) In the proposed study, Connect-Home structure and processes provide a robust foundation for adapting transitional care for persons with ADRD and their caregivers.

The study, described in this protocol, builds on a completed, systematic adaptation of Connect-Home to align with the Alzheimer's Association "Practice Recommendations for Person-Centered Care" and address unmet care needs of persons with ADRD.(20) Numerous frameworks describe adaptation as a systematic progression using steps required to modify an intervention to fit the needs of new populations or contexts and ensure acceptability to key stakeholders.(21) A central goal of adaptation is to modify the form of the intervention (i.e., structure), while maintaining fidelity to its underlying program theory.(21) Consistent with this goal, we modified Connect-Home structures (plan of care template, toolkit, training) while retaining the underlying program theory. We modified structures with the goal of building staff capacity to tailor the existing set of six Connect-Home transitional care processes to the distinct needs of persons with ADRD and their caregivers. In doing so we retained fidelity to the program theory, which hypothesizes that the six key processes are the causal mechanisms through which Connect-Home improves patient and caregiver outcomes.(1, 22) Thus, for example, the adaptation of Connect-Home added elements to the EHR template for the Transition Plan of Care (structure) to prompt for staff to tailor coordination of medical care (key process) to include needed referrals for dementia follow-up care.(16, 23) Another adaptation was to modify the Connect-Home training protocol (structure) and add staff training content on tailoring care plans for symptom management (key process), with guidance for needed home-based care of neuropsychiatric symptoms such as withdrawal, agitation, and resistance to care. Our approach to adaptation followed the five steps described by Chen et al. (2013).(24) This included: learning from staff in SNFs with four years of experience using the un-adapted version of Connect-Home, convening a steering committee, determining the fit of Connect-Home with the transitional care needs of persons with ADRD and their caregivers, summarizing findings and create a list of unmet needs, and making choices about how to adapt Connect-Home to address unmet needs.

The objective of this study is to test the feasibility and acceptability of the adapted intervention (Connect-Home Plus) in a total sample of 20 patients and 20 caregivers in two SNFs. The rationale for this study is that testing Connect-Home Plus will generate a new model of transitional care for a future trial. The specific aim is to determine the feasibility and acceptability of the adapted version of Connect-Home (primary outcomes) and estimated mean outcomes of persons with ADRD and their caregivers (secondary outcomes, i.e., preparedness for discharge, quality of life, hospital readmission, and caregiver burden).

#### 4. STUDY OBJECTIVES

the objective of this study is to test the feasibility and acceptability of the adapted intervention (Connect-Home Plus) in a total sample of 20 patients and 20 caregivers in two SNFs.

**Primary Objective:** Determine the feasibility and acceptability of the adapted version of Connect-Home.

**Secondary Objective:** Determine estimated mean outcomes of persons with ADRD and their caregivers, e.g., preparedness for discharge, quality of life, hospital readmission, and caregiver burden).

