Study Objective(s)	
Primary
 

• Feasibility of the intervention. The feasibility items include: (1) completing the Transition Plan of Care; (2) convening the care plan meeting with caregiver attending; (3) reviewing advance directives in the SNF; (4) scheduling follow-up medical appointments; (5) transmitting records to follow-up clinicians; (6) home care nurse completion of the first home visit within 24 hours after discharge; (7) completion of first caregiver support call within 72 hours of discharge; (8) completion of the second and third caregiver support call within one month of discharge.

• Patient satisfaction with services, including services were easy or difficult to use, supports were or were not helpful, and services helped to manage issues related to ADRD at home.

• Mean caregiver intervention satisfaction scores, including services were easy or difficult to use, supports were or were not helpful, and services helped to manage issues related to ADRD at home.

 
Secondary

- 
- Patient preparedness for discharge will be measured by the Care Transitions Measure-15 (CTM-15), which measures self-reported knowledge and skills for continuing care at home.
  - Caregiver preparedness for caregiving will be measured by the Preparedness for Caregiving Scale (PCS), which measures self-reported readiness for caregiving.
  - Patient function will be measured using the Life Space Assessment, where scores are the product of the "Life-space level" (range 1-5) and the "independence" score (range 1-2).
  - The quality of life of the patient will be assessed with the Dementia Quality of Life Measure.
  - When the patient is unable to rate their quality of life, the quality of life will be rated by their caregiver, using the Dementia Quality of Life-Proxy measure.
  - Patient-reported Days of Emergency Department or Hospital Use 30 Days After Skilled Nursing Facility Discharge.
  - Caregiver burden will be measured using the Zarit Caregiver Burden Scale, measuring caregiver perceptions that "caregiving has an adverse effect on their emotional, social, financial, physical and spiritual functioning."
  - Caregiver distress will be measured using the Distress Thermometer.
- 

**Test Article(s)  
(If Applicable)**

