- Dementia Quality of Life-Proxy measure (DEMQOL-Proxy). When the patient is unable to rate their quality of life, the quality of life will be rated by their caregiver, using the Dementia Quality of Life-Proxy measure.(33) The score range is 31-124 with higher scores indicating better quality of life.
- Self-Reported Days of ED or Hospital Use 30 Days After Skilled Nursing Facility Discharge. Patient's days of acute care use will be measured using the self-reported number of combined number of days the patients pends in the Emergency Department (ED) or hospital in 30 days after SNF discharge.(19)
- Zarit Caregiver Burden Scale. Caregiver burden will be measured using the Zarit Caregiver Burden Scale, which includes 12 items on a five-point scale, measuring caregiver perceptions that "caregiving has an adverse effect on their emotional, social, financial, physical and spiritual functioning."(34) Scores range 0-48; higher scores are associated with depression and social isolation.
- Distress Thermometer. Caregiver distress will be measured using the Distress Thermometer, which includes 1 item on an 11-point scale, measuring negative affect (e.g., sadness and fear) related to caregiving for a severely ill person. Score ranges 0-10, with scores >4 associated with poor coping and depression.(35)

a. Safety Evaluations

- Study progress and safety will be reviewed monthly (and more frequently if needed). Progress reports will include patient and caregiver recruitment, retention/attrition, and adverse events. In addition, safety evaluation will include (1) whether adverse event rates are consistent with pre-study assumptions; (2) reason for dropouts from the study; (3) whether all participants met entry criteria; (4) whether continuation of the study is justified on the basis that additional data are needed to accomplish the stated aims of the study; and (5) conditions whereby the study might be terminated prematurely.
- An adverse event (AE) is any untoward medical occurrence in a subject temporally associated with participation in the clinical study or with use of the experimental agent being studied. An adverse finding can include a sign, symptom, abnormal assessment or any combination of these. A Serious Adverse Event (SAE) is any adverse event that results in one or more of the following outcomes:
  - Death
  - A life-threatening event
  - Inpatient hospitalization
  - A persistent or significant disability/incapacity

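### Hospital readmission is a named secondary outcome, but the only acute-care measure is a combined count of ED and hospital days, which cannot yield a readmission rate and has no rule for deaths

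*Combined protocol and SAP*

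**What the plan says.** The specific aim, at the end of Section 3 (Relevant Literature and Data), lists the "secondary outcomes, i.e., preparedness for discharge, quality of life, hospital readmission, and caregiver burden". Section 4 asks the study to "Determine estimated mean outcomes of persons with ADRD and their caregivers" and gives "hospital readmission, and caregiver burden" among its examples.

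The outcome list in Section 7 defines one acute-care measure: the "self-reported number of combined number of days the patients pends in the Emergency Department (ED) or hospital in 30 days after SNF discharge". The synopsis has the same construct: "Patient-reported Days of Emergency Department or Hospital Use 30 Days After Skilled Nursing Facility Discharge". Neither place defines a readmission indicator, a count of admissions, or a split between ED and inpatient days. Section 3 (Risks, psychological) mentions a third construct, time at home free of acute care, which does not reappear in the outcome list.

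For analysis, the synopsis and Section 8 (Statistical Methods) promise descriptive statistics for acute care use and name no particular statistic. Death appears in Section 7 as a serious adverse event criterion and in Section 10 under reporting. No section says how it affects this outcome.

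**The concern.** Someone who follows the plan as written would finish with a number of days per patient and a mean of those days. The aim and objective promise hospital readmission. A day count that pools ED and inpatient time does not show who was readmitted, and its mean shows it even less. The study could therefore be completed without reporting an outcome that its own aim names.

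The second issue is death. Section 3 describes SNF patients as typically frail and seriously ill, so a death within 30 days of discharge is plausible, although the documents give no rate. A day count with no rule for death does not separate a patient who stayed well at home from one who died there.

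**Working it through.** **Inputs from the documents.** n = 20 patients (Sections 5c and 8). Outcome: combined ED and hospital days over 30 days (Section 7). Summary: the mean (Section 4). Background rate: "23% of persons with ADRD experienced rehospitalization within 30 days of returning home" (Section 3). The plan gives no precision target, SD or expected number of days, so it has no figure of its own to reproduce. The day counts below are hypothetical and serve only to show what the measure can distinguish.

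**1. Can the mean of combined days recover readmission?** Mean = total days / 20.

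| Hypothetical sample of 20 | Total days | Mean | Median | Readmitted |
|---|---|---|---|---|
| One patient with 20 hospital days | 20 | 1.0 | 0 | 1/20 = 5% |
| Five patients with 4 hospital days each | 20 | 1.0 | 0 | 5/20 = 25% |
| Twenty patients with 1 ED-only day each | 20 | 1.0 | 1 | 0/20 = 0% |

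The mean is the same for three different readmission rates. The median does not solve the problem either, since the first two rows share a median of 0. Only a separate readmission item distinguishes the rows.

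**2. What would a proportion give?** At the 23% background rate, 20 × 0.23 = 4.6 readmitted patients are expected, and the chance of at least one is 1 − 0.77^20 = 0.995. The exact (Clopper-Pearson) 95% limits for x of n are the 2.5% quantile of Beta(x, n − x + 1) and the 97.5% quantile of Beta(x + 1, n − x):
- 4/20: 5.7% to 43.7%
- 5/20: 8.7% to 49.1%

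These intervals are wide, but they describe the outcome that the aim names.

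**3. What does an unstated death rule do?** Assume five survivors with 4 days each (20 days in total) and, among the other 15, d deaths at home on day 2 without acute care.

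| d | Mean days, deaths entered as 0 | Mean days, deaths excluded | Mean days alive and out of acute care (of 30) |
|---|---|---|---|
| 0 | 20/20 = 1.00 | 20/20 = 1.00 | 29.0 |
| 1 | 20/20 = 1.00 | 20/19 = 1.05 | 27.6 |
| 2 | 20/20 = 1.00 | 20/18 = 1.11 | 26.2 |
| 3 | 20/20 = 1.00 | 20/17 = 1.18 | 24.8 |

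The last column is (5 × 26 + (15 − d) × 30 + 2d) / 20. For d = 1 this is (130 + 420 + 2)/20 = 27.6.

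If the early deaths fall instead among the five patients who would have been readmitted, and are entered as 0, the mean is 4 × (5 − d)/20. It goes from 1.0 to 0.8, 0.6 and 0.4 for d = 1, 2 and 3, so the result looks better as more patients die. Days alive and out of acute care move in the right direction with each death.

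**The case against.** The strongest reply is that the mismatch is loose wording in a small descriptive pilot. Section 4 offers its list only as examples. The operational text is broadly consistent in speaking of acute care use, as does the description of the parent trial. Death and inpatient hospitalization are both serious adverse event criteria, events are sought at the 7-, 21- and 30-day calls, and adverse events will be summarised. Part of this stands: admissions and deaths should surface in the safety data. They would surface there as safety events, however, not as the secondary outcome. The specific aim presents its list as the secondary outcomes themselves, not as examples. The chart abstraction does not fill the gap, because Section 7 draws it from the SNF record and lists no admissions after discharge.

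Four stronger readings are tempting, and the documents do not support them:
- **That the plan scores an early death as the best outcome.** No section says so. A patient who dies before the call cannot self-report. The caregiver fallback could lead to a 0, to days up to death, or to a missing value. The definition permits a 0 but does not impose it.
- **That only a mean will be reported.** The mean comes from the aim and objective. Section 8 says descriptive statistics, which leaves room for medians and proportions.
- **That about 15 of 20 patients will have zero days.** This applies the 23% rehospitalization rate to a measure that also counts ED days. The documents give no ED rate.
- **That this figure will size a later trial or be compared with 23%.** Neither is planned. Section 3 (Potential Benefits) rests the case for a later trial on feasibility and acceptability.

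**Conclusion.** The concern holds in this form: the aim and objective name hospital readmission, and the one acute-care measure defined cannot deliver it. This follows from the definitions and needs no assumption about event rates. The illustration at n = 20 shows readmission of 0%, 5% and 25% behind the same mean of 1.0 day.

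The gap over deaths is real but secondary, and taken alone it would be a missing detail. Its numerical effect depends on assumed deaths and on how they happen to be entered.

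The consequence is limited to one secondary outcome in a single-arm descriptive study. No test, power calculation or primary conclusion depends on it. It is still worth correcting before data collection, because a pooled total cannot be separated afterwards except through the safety records.

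**What to change.** 1. At the existing day-30 call, record hospital admissions and ED visits as separate items, and cross-check admissions against the serious adverse event records.
2. In Sections 7 and 8, define hospital readmission as an outcome. Report the number and proportion of patients with at least one readmission, and separately with at least one ED visit, each with an exact 95% confidence interval.
3. Report acute-care days as median and range alongside the mean.
4. Report deaths beside this outcome. Use days alive and out of ED or hospital, of 30, as the day-based summary, with days after death counted as 0. This is close to the construct already mentioned under psychological risks in Section 3. It is a reasonable choice, not the only one; what matters is that a rule is written down in advance.
5. Word the aim, objective, synopsis and outcome list alike.

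The call window is ±7 days, so a call may fall as early as day 23. Record the call date, so that a 30-day figure is not reported for a period that was only partly observed.

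Cost: one or two added questions on a call that already takes place, a few summary lines, and edits to the text. If the day-30 form already asks about admissions and ED visits separately, which the documents do not show, only the reporting changes. No extra patients or visits are needed.
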